A single interim analysis for re-hospitalization-free survival will be performed using O'Brien-Fleming boundaries for benefit or harm when 50% of expected person time (350 child-years) has been accrued. Assuming 157 events will be available at half of the person-time accrual, a z-score critical value of 2.797, or p -value < 0.005 , from a Kaplan Meier log-rank test will determine the cut-off of statistical significance. A symmetric boundary will be used for benefit or harm. The DSMC will review this analysis and make a determination about continuing the study. Futility will not be a basis for stopping rules because of the trials' value in understanding mechanisms of post-discharge worsening and antibiotic resistance. Assuming the DSMC decides to continue the trial after the interim analysis, an alpha of 0.045 will be used as the statistical significance boundary at the final analysis for the primary hypothesis test.

Timing of Final Analysis

The first main report/ publication of the trial will be prepared for the primary aim when every enrolled child has completed their 6 month follow-up visit or is deemed lost to follow-up and all primary endpoint data has been cleaned (anticipated publication in September 2020).

Timing of Outcome Assessments

The schedule of study procedures is outlined in Table 1. Regularly scheduled visits include those at M0 (hospital discharge), M3, and M6. Participants are actively followed for 1 month following their missed visit. If a visit occurs after the one month window, relevant data will be ascertained when possible, but may not be included in the analysis (as described in Table 1). The start date/time for each participant is the date/time of randomization.

Table 1. Allowable windows for each outcome

Outcome	Visit Window
Death or re-hospitalization	Follow-up time censored 180 days after enrollment or at the time of the last follow-up visit (if < 180 days). Data collected (including vital status) from visits that occur beyond 180 days will be included but events and person-time will be censored at 180 days.
Cause specific hospitalization	Follow-up time censored 180 days after enrollment or at the time of the last follow-up visit (if < 180 days). Data collected (including vital status) from visits that occur beyond 180 days will be included but events and person-time will be censored at 180 days

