Prevalence of Shigella , Salmonella , Campylobacter , Cryptosporidium , Giardia @ enrollment, day 90, and day 180	Visits that occur within 30-days on either side of 90-days (M3) and 180-days (M6) visits will be included. Therefore, visits occurring outside of 60-120 days post-enrollment for M3 and outside of 150-210 days post enrollment for M6 will be excluded from the primary analysis but included in sensitivity analyses.
Streptococcus pneumoniae (S. pneumoniae) prevalence @ enrollment, day 90, and day 180	Visits that occur within 30-days on either side of 90-days (M3) and 180-days (M6) visits will be included. Therefore, visits occurring outside of 60-120 days post-enrollment for M3 and outside of 150-210 days post enrollment for M6 will be excluded from the primary analysis but included in sensitivity analyses.
Prevalence of resistance to azithromycin in E.coli and S. pneumoniae and prevalence of ESBL-producing E.coli @ enrollment, day 90, and day 180	Visits that occur within 30-days on either side of 90-days (M3) and 180-days (M6) visits will be included. Therefore, visits occurring outside of 60-120 days post-enrollment for M3 and outside of 150-210 days post enrollment for M6 will be excluded from the primary analysis but included in sensitivity analyses.

SECTION 4. STATISTICAL PRINCIPLES

Confidence Intervals and P values

Level of statistical significance

All statistical tests will be 2-sided using a 5% significance level (alpha of 0.05). For the primary aim (aim 1), an alpha of 0.045 will be used for hypothesis tests that were part of the interim analysis to account for alpha spending.

Type I errors

We will not adjust the alpha for multiple testing in the primary aim. Instead we will clearly state primary and secondary analyses and interpret secondary analyses as hypothesis-generating rather than confirmatory. All secondary aims will be adjusted for multiple comparisons using the Benjamini and Hochberg method using a false discovery proportion of 0.05.

Confidence intervals to be reported

For the primary analysis of Aim 1, two-sided 95.5% confidence intervals will be used to account for the 0.045 alpha spent at the interim analysis. All other analyses will utilize two-sided 95% confidence intervals.

Adherence and Protocol Deviations

Definition of adherence to intervention and how this is assessed including extent of exposure

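### The final alpha of 0.045 comes from subtraction and does not match the O'Brien-Fleming interim value of 2.797, whose partner is 0.048; the error is small and conservative

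*SAP*

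**What the plan says.** SAP Section 3 (Statistical Interim Analysis and Stopping Guidance) plans a single look for benefit or harm "using O'Brien-Fleming boundaries for benefit or harm when 50% of expected person time (350 child-years) has been accrued". The boundary is symmetric and there is no futility stopping. The critical value is given as follows: "Assuming 157 events will be available at half of the person-time accrual, a z-score critical value of 2.797", which the SAP equates to p < 0.005. If the trial continues, "an alpha of 0.045 will be used as the statistical significance boundary at the final analysis for the primary hypothesis test".

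SAP Section 4 sets a general two-sided level of 5%, repeats 0.045 for the Aim 1 tests that were part of the interim analysis, and carries it into the interval: "For the primary analysis of Aim 1, two-sided 95.5% confidence intervals will be used". The reason it gives is that 0.045 was spent at the interim.

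The SAP revision history places the stopping rules and the final alpha boundary in version 2.0 (March 2016), before the interim. Version 5.0 (May 2020) came after an interim that used data through 31 October 2018, and before unblinding.

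**The concern.** A two-look O'Brien-Fleming design fixes both critical values together. Once the interim value is 2.797 at half information, the final value follows from the joint distribution of the two test statistics. The SAP takes its interim value from that design, but its final value looks like what is left after subtracting the interim p-value from 0.05.

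The affected number is the decision threshold for the primary hypothesis. A primary p-value between 0.045 and 0.048 would be declared non-significant, although the boundary named for the interim would support significance. The confidence level of the headline hazard ratio inherits the same figure. The stated reason for the 95.5% interval also confuses the alpha spent with the alpha left over.

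**Working it through.** **Inputs.** Overall two-sided alpha 0.05 (SAP Section 4). One interim at 50% with z = 2.797, then final alpha 0.045 (SAP Section 3). Hazard ratio 0.70, 22.5% incidence, 1,100 children needed and 1,400 enrolled (protocol, Sample Size, Aim 1). Follow-up censored at 180 days (SAP Table 1) and ended by the first re-hospitalization or death (SAP Section 6). A 20% loss allowance (protocol, Sample Size, Aim 3).

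**1. The planning figures that reproduce.**
- Person-time: 1,400 × 0.5 year = 700 child-years; half is 350.
- Events: 1,400 × 0.225 = 315; half is 157.5, given as 157.
- Sample size: Schoenfeld's formula at hazard ratio 0.70, alpha 0.05 and power 0.80 gives 247 events; 247 / 0.225 = 1,098, or 549 per arm, against the stated 550.

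**2. The boundary.** With information fraction t, the two statistics are approximately bivariate normal with correlation √t, and

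overall error = 1 − P(|Z1| < c1, |Z2| < c2).

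O'Brien-Fleming sets c1 = c2 / √t. Solving for overall error 0.05 at t = 0.5 gives c2 = 1.9774 and c1 = 1.9774 × √2 = 2.7965.
- Interim: two-sided p = 0.0052. The SAP's 2.797 reproduces.
- Final: two-sided p = 0.0480. The SAP's 0.045 does not reproduce.

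Lan-DeMets spending of O'Brien-Fleming type at t = 0.5 gives 0.0031 and 0.0490, so it does not yield 0.045 either. Of the routes tried, only 0.05 − 0.005 = 0.045 does.

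**3. Overall error as written.** A final alpha of 0.045 is z = 2.005. With c1 = 2.797, c2 = 2.005 and t = 0.5, the overall error is 0.0471.

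**4. Cost.**
- Interval width: 2.0047 / 1.9774 = 1.014, so 1.4% wider.
- Power (fixed-sample approximation): Φ(|ln 0.70| × √E / 2 − z). With E = 1,100 × 0.225 = 247.5, the first term is 0.3567 × 15.73 / 2 = 2.806. Then Φ(2.806 − 1.977) = 79.6% and Φ(2.806 − 2.005) = 78.8%. With 315 events the figures are 88.3% and 87.7%.

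**5. Sensitivity to timing, with 2.797 held fixed.** The final alpha that keeps 0.05 overall is:

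| t | final alpha | overall error using 0.045 |
|---|---|---|
| 0.30 | 0.0467 | 0.0483 |
| 0.50 | 0.0480 | 0.0471 |
| 0.60 | 0.0486 | 0.0464 |
| 0.80 | 0.0497 | 0.0453 |

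The value 0.045 is conservative at each of these fractions.

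**6. Secondary check: is 350 child-years half?** It is half of 700, which assumes that no child has an event or is lost. With a constant hazard h = −ln(1 − 0.225) / 0.5 = 0.510 per year, time at risk per child is 0.225 / 0.510 = 0.441 year, and 1,400 children give about 618 child-years. Applying hazard ratio 0.70 in one arm gives about 630. So 350 is 350 / 630 = 56% to 350 / 618 = 57% of expected person-time. With 20% loss at a constant rate the totals are 556 to 566, and 350 is 62 to 63%.

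**The case against.** The strongest reply is that a pre-specified threshold stricter than necessary still gives a valid test. There is no type I inflation and no bias. Under the planned effect, the chance that p falls between 0.045 and 0.048 is the power difference in step 4, under 1%. Section 3 attaches the O'Brien-Fleming name to the interim look and gives 0.045 separately, without calling it the O'Brien-Fleming final value. Moreover, the threshold was set before the interim, and the trial statistician, who is the SAP's senior responsible statistician, was not blinded at that look. Relaxing it afterwards invites suspicion.

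Most of this stands. It makes the point minor and limits how the fix may be made. It does not make the figure right: Section 4 presents 0.045 as accounting for alpha spending, nowhere labels it a deliberate conservative choice, and misstates what was spent.

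A reader might also infer that the mistimed look causes the strictness. It does not: the gap is already there at exactly 50%. If the O'Brien-Fleming boundaries were recomputed for a look at 57%, the final p would be about 0.0469, closer to 0.045, but the interim value would no longer be 2.797. With 2.797 kept, a later look only widens the gap slightly.

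A reader might further infer that 350 child-years would yield many more than 157 events. Under a constant hazard that needs 22.5% in both arms (350 × 0.510 = 178). SAP Section 3 gives 22.5% as the placebo incidence and the protocol plans hazard ratio 0.70; those inputs give 272 × 350 / 630 = 151, close to 157. Higher counts need a front-loaded hazard whose shape the documents do not give.

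**Conclusion.** The final alpha of 0.045 and the 95.5% interval do not go with an interim value of 2.797 at half information; 0.048 and 95.2% do. The consequences are an overall error of about 0.047, an interval about 1.4% too wide, and about 0.8 points of power. The error is conservative and minor, and it does not threaten the validity of the primary test.

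The value 0.048 is exact only for a look at t = 0.5 and relies on the usual correlation of √t between looks, which is approximate here because the interim uses a log-rank test and the final a site-adjusted Cox model. The power figures assume 247.5 events and hazard ratio 0.70.

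The person-time remark is secondary. The 56 to 57% (no loss) and 62 to 63% (20% loss) figures assume constant hazards, and the actual interim event fraction is not in the documents.

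**What to change.** In a dated SAP revision before unblinding, do one of the following.

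- **Preferred:** replace 0.045 with 0.048 and 95.5% with 95.2% in Sections 3 and 4, stating that both follow from the pre-specified 2.797 at the planned 50% look. If the team prefers the actual interim event fraction, hold 2.797 fixed and have the calculation done by someone who has not seen results by arm.
- **If the team does not wish to relax a threshold after the interim:** keep 0.045 and 95.5%, and say plainly that this is a conservative split with overall alpha of about 0.047.

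Either way, correct the Section 4 sentence on the interval: about 0.005 is spent at the interim. Align the Table 3 column, which is headed 95% CI, with the level chosen. Add one sentence saying that 350 child-years is half of the nominal 700, before time at risk is shortened by events and losses.

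The cost is a few numbers, two or three sentences and one short calculation. The first option also needs a recorded justification, because it changes a threshold after the interim look.

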Analysis of primary outcomes will be by modified intention-to-treat (mITT). The mITT population will include all randomized children according to the treatment they were randomized to receive but will exclude those who were deemed ineligible, post-randomization. In per-protocol analyses (secondary to the mITT), we will compare treatment effects in groups defined by self-reported adherence to the 5-day course of azithromycin. Per protocol analyses will also exclude children who were ineligible, those who were lost to follow-up, and those who withdrew consent.

SECTION 5. TRIAL POPULATION

Screening Data

The total number screened will be reported along with summary of reasons for exclusion into the trial.

Eligibility

Children age 1 to 59 months old who weigh at least 2 kg and have been hospitalized and subsequently discharged from hospitals in Kisii or Homa Bay County for conditions other than trauma, injury, poisoning, or a birth defect, will be eligible for the RCT (Aim 1). We will exclude children in whom azithromycin is contraindicated (children taking or prescribed other macrolide antibiotics, such as erythromycin or clarithromycin, or the protease inhibitor lopinavir); those with a known macrolide allergy, those who do not plan to remain in the study site catchment area for at least 6 months, those without a legal guardian or a legal guardian does not provide consent, those with a twin is eligible and enrolled in the trial on the same day, those that are being referred to another facility, and those with a caregiver who is unwilling to participate in contact cohort if selected (willing/able to provide a stool and nasopharyngeal sample at enrollment, 90 days and 6 months of follow-up if randomized to the Contact Cohort).

Recruitment

Per CONSORT guidelines, we will report the number of individuals who:

1. Underwent screening
2. Met inclusion criteria
3. Did not meet inclusion criteria (and reasons)
4. Enrolled in the study and were randomized

5. Were included in the mITT
6. Were included in the per-protocol population

Withdrawal/Follow-Up

Level of withdrawal (e.g. from intervention and/or from follow-up)

Withdrawal of consent will be tabulated using the following categories: withdrawal from follow-up but allow prior collected data/ samples to be used; withdrawal from follow-up and disallow already collected data/samples to be utilized; withdrawal from study intervention but continue with follow-up/data collection; withdrawal from study intervention and discontinue with follow-up/data collection.

Timing of withdrawal/lost to follow-up data

Tabulation of withdrawals will include withdrawals by each follow-up timepoint (M3 and M6).

Reasons and details of how withdrawal/lost to follow-up data will be presented

The numbers and reasons (if available) of losses to follow-up (withdrawals or losses to follow-up) will be summarized by treatment arm.

Baseline Patient Characteristics

Baseline characteristics and how they will be descriptively summarized

We will describe the distribution of baseline characteristics (outlined in Table 2), using summary statistics appropriate for the measurement scale (median and interquartile range [IQR] or n and %). We will present these summary statistics in tables by randomization arm as outlined in Table 2. No statistical tests comparing baseline characteristics by randomization arm will be conducted, but the clinical importance of any appearing imbalance will be noted.

Table 2 Baseline characteristics shell table

Characteristic	All (N=) n(%) Median(IQR)	Azithromycin-treated group (N=) n(%) Median (IQR)	Placebo-treated group (N =) n(%) Median(IQR)
Site			
Kisii Teaching & Referral Hospital			
Homa Bay County Referral Hospital			
St. Paul Mission Hospital			
Kendu Adventist Hospital			
Sociodemographic			
Age			
1m to 5m			
6m to 11m			
12m to 23m			
24m to 59m			
Median age (months)			
Female			
Extreme poverty (household income < \$1.90 USD / day)			
Primary caregiver education ≤ primary school			
Household Living Conditions			
Crowding (≥2 people per room living in house)			
Unimproved water source (well/spring/surface water)			
Reports treating drinking water			
Toilet Type			
Flush			
Pit Latrine			
Open Defecation			
Admission History			
Discharge diagnoses as reported in medical record			
Anemia			
Gastroenteritis/diarrhea			
Lower Respiratory Tract Infection			
Malaria			
Malnutrition			
Meningitis			
Sepsis			
Sickle Cell			
Tuberculosis			
Other			
Not recorded in hospital record			
Duration of hospital admission (days)			
Left against medical advice			
Received antibiotics in hospital			
Prescribed antibiotics at discharge			
Nutritional, HIV, and Vaccine Status			
Breastfeeding status (in first 6 months of life)			
Exclusively breastfed			
Partially breastfed			
Never Breastfed			
Unknown			
Stunted (HAZ < -2)			

Underweight (WAZ < -2)			
Acute Malnutrition			
Severe (WHZ < -3 or MUAC <11.5cm or edema)			
Moderate (-3 ≥ WHZ < -2 or 11.5 ≥ MUAC <12.5cm)			
HIV-status			
HIV- infected			
HIV-exposed, uninfected			
HIV-exposed, unknown infection status			
HIV status unknown			
Received all age-appropriate vaccines			

SECTION 6. ANALYSIS

Outcome Definitions

Primary study end-points:

1. **Deaths** will be ascertained by study staff either through community health workers, hospital staff, or determined at follow-up visits. Date of death will be ascertained from the following (in order of prioritization): death certificate, hospital record, caregiver report
2. **Re-hospitalization** will be assessed by questionnaire at day 90 and 180 follow-up visits and medical record review. In cases when both sources are available, information from the medical record will be considered the gold standard. A hospitalization will be defined as an overnight stay, including situations where a child is admitted in the middle of the night (even if after midnight) and discharged the subsequent morning. Re-hospitalizations that are a continuation of management from the previous hospitalization (such as elective blood transfusion) or that occur during enrollment procedures, due to a clinical deterioration post-discharge, will be excluded from the analysis. To operationalize these exclusions, we will exclude re-hospitalizations that occur <2 hours after administration of the study medication and those re-hospitalizations that occur as a result of the child being advised to seek further care for a blood transfusion due to a lack of blood availability at the enrollment facility.
3. **Loss to follow-up** will be defined as non-attendance at both follow-up visits despite up to one month of active tracing and no clear evidence of death.
4. **Death or re-hospitalization** (combined) is the primary endpoint.

Secondary end-points:

5. **Cause-specific deaths** will be determined by consensus among clinical investigators based on all available information (death certificate, medical records, physical exams performed as part of study procedures, and verbal autopsies). Verbal autopsies will also be performed using the Population Health Metrics Research Consortium Shortened Verbal Autopsy Questionnaire. Secondary to the cause-assignment by consensus, we will additionally determine cause using the SmartVA-Analyze tool applied to the Verbal Autopsy form which utilizes the Tariff 2.0 Method to assign cause.^[7] Causes assigned by the verbal autopsy tool will be reported secondary to the consensus-assigned cause because the information utilized for cause of death by consensus is likely to exceed that captured by the verbal autopsy questionnaire asked to the caregivers.
6. **Cause-specific re-hospitalizations** will be assessed by questionnaire (maternal recall of diagnosis) at day 90 and 180 follow-up visits and medical record review (discharge diagnosis).

In cases when both sources are available, information from the medical record will be prioritized. Because children can have more than one diagnosis, each diagnosis (diarrhea, pneumonia, malnutrition, or malaria) will be considered in separate analyses. Additionally, we will consider a combined diagnosis of diarrhea, pneumonia, malnutrition and/or malaria to capture the diagnoses we hypothesize to be more affected by azithromycin.

1. **Bacterial pathogen carriage** will be assessed based on microbiologic testing of stool/rectal swabs and nasopharyngeal swabs at 90 and 180-day follow-up visits. *Shigella*, *Salmonella*, and *Campylobacter* will be assessed in the stool and *Streptococcus pneumoniae* (*S. pneumoniae*) will be assessed in nasopharyngeal swabs.
